6.2.2 Death Dates

If death year and month are available but day is missing:

• If mmyyyy for last contact date = mmyyyy for death date, set death date to the day after the

last contact date.

• If mmyyyy for last contact date < mmyyyy for death date, set death date to the first day of

the death month.

If mmyyyy for last contact date > mmyyyy for death date, data error and do not impute.

If both month and day are missing for death date or a death date is totally missing, do not impute

and censor the subject's survival time.

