5.5.4 Analysis of Efficacy Parameters

Overall Response Rate

ORR will be defined as the proportion of subjects who achieve a CR or PR according to the Lugano Classification for NHL (Cheson et al. 2014), as assessed by investigators. ORR will be calculated, and the corresponding 2-sided confidence interval will be derived.

Duration of Response

The DOR is defined as the interval from the first documentation of CR or PR to the earlier of the first documentation of definitive disease progression or death from any cause. Kaplan-Meier methods will be used to estimate event-free curves and

corresponding quantiles (including the median).

Progression-Free Survival

PFS is defined as the interval from the start of acalabrutinib therapy to the earlier of the first documentation of objective disease progression or death from any cause. Kaplan-Meier methods will be used to estimate the event-free curves and corresponding quantiles (including the median).

Time-to-Next Treatment

Time-to-next treatment defined as the time from start of acalabrutinib therapy on this protocol to the start of the next treatment. Kaplan-Meier methods will be used to estimate the event-free curves and corresponding quantiles (including the median). Data from subjects who have not received subsequent therapy will be censored at the earliest of death or the last time that lack of administration of a new therapy was objectively documented.

Time-to-next treatment data will be collected from subjects in Part 2 and Part 3 for an exploratory analysis.

Overall Survival

The duration of OS will be measured from the start of acalabrutinib therapy until the date of death. Subjects who are known to be alive as of their last known status will be censored at their date of last contact. Kaplan-Meier methodology will be used to estimate OS curves and corresponding quartiles (including the median).

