#### 7.6.4 Overall Survival

The duration of OS will be measured from the first dose date of any study drug until the date of death due to any cause. Subjects who were not known to have died prior to the analysis data cutoff date will be censored as detailed in Table 2.

Table 2. Overall Survival Censoring

Situation	Date of Event or Censoring	Outcome
Death before first disease assessment	Date of death	Event
Death between scheduled assessments	Date of death	Event

\*Assessment is adequate if it is not "Unknown/NA" or missing

All other cases will be censored as follows:			
Lost to follow-up immediately after	Randomization date	Censored	
randomization			
Not known to have died at or prior	Date last known alive before analysis	Censored	
to analysis data cutoff date	data cutoff date		
Known to have died, but death	Date last known alive before death	Censored	
date is missing month and day or			
is completely unknown			
Not known to have died prior to	Date last known alive before lost to	Censored	
lost to follow-up or study exit	follow-up or study exit		

OS will be calculated as death date (or censoring date) – first dose date of any study drug + 1.

OS will be analyzed in the same fashion as that for primary efficacy endpoint as described for PFS in Section 7.6.3.

If at least 1 subject has an event of death due to COVID-19, a sensitivity analysis will be conducted to assess for the potential impact of deaths due to COVID-19. Subjects with death related to COVID-19 infection will be censored at their date of death due to COVID-19.

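### SAP 6.2.2 and Table 2 censor a known death when its month and day, or its whole date, is missing; any such case biases overall survival upward

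*SAP*

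**What the plan says.** Protocol 5.5.4 defines the endpoint: "The duration of OS will be measured from the start of acalabrutinib therapy until the date of death". On censoring it says: "Subjects who are known to be alive as of their last known status will be censored at their date of last contact". It says nothing about a subject who is known to have died but whose date of death cannot be established.

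SAP 6.2.2 covers incomplete death dates in two tiers.

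- **Only the day missing.** The date is imputed. For a last contact in the same month, the death is placed one day later than that contact ("If mmyyyy for last contact date = mmyyyy for death date, set death date to the day after the"); if last contact was in an earlier month, the first day of the death month is used.
- **Month and day missing, or no date at all.** "If both month and day are missing for death date or a death date is totally missing, do not impute". The consequence for OS is stated in the same sentence: "and censor the subject's survival time".

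SAP Table 2 (Section 7.6.4) repeats the second tier in the row that begins "Known to have died, but death". The outcome is censored and the date is given as "Date last known alive before death". The two places agree, so the rule is deliberate.

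Another row of Table 2, which begins "Lost to follow-up immediately after", censors at a randomization date. This SAP covers Parts 2 and 3 only, neither is described as randomized, and Section 7.6.4 counts OS from the first dose of any study drug.

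**The concern.** For these subjects the event is certain and only its date is not. Censoring them removes the event and keeps the uncertainty out of sight. The subject is censored because he or she died, so the censoring is informative, and Kaplan-Meier estimation assumes that it is not. The expected error has one direction: survival looks better.

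The rule also sits badly with the SAP's other date rules. A death with only the day missing is dated. A year-only date is imputed to 30 June for adverse events, medications, anticancer therapy and diagnosis (6.2.1), and to 1 January for the date last known alive (6.2.3). For a death, the year is discarded and the event with it.

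At stake is a secondary endpoint of both parts, in cohorts small enough for one lost event to show in the reported estimate.

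**Working it through.** The plan states no OS rate and no death count, so there is no figure of its own to reproduce. The size below is an illustration.

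**Inputs**

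- n = 40, the maximum for Part 2 Cohort 1, and n = 26, the lower end for Part 3 (Protocol 5.2).
- Projected median follow-up of about 30 months in Part 2 (Protocol 3.2) and contact about every 12 weeks (Protocol 4.4).
- D deaths by the time point: *assumed* 4, 6 or 8. Undated deaths: *assumed* one. Neither is in the documents.
- Everyone else is followed past the time point.

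**Step 1, all deaths dated.** S = (n − D)/n.

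**Step 2, the SAP rule.** Suppose the undated death is j-th in order when it is censored. The estimate before it is (n − j + 1)/n. After it, n − j remain at risk and D − j deaths follow, which contributes (n − D)/(n − j). Hence

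S′ = S × (n − j + 1)/(n − j), and the gain is S/(n − j).

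The gain is smallest at j = 1, where it is S/(n − 1), and largest at j = D, where it is 1/n. For n = 40, D = 4, j = 3: 0.90 × 38/37 = 92.4%.

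| n | D | All dated | SAP rule, j = 1 | SAP rule, mid-series | SAP rule, j = D | Gain (points) |
|---|---|---|---|---|---|---|
| 40 | 4 | 90.0% | 92.3% | 92.4% (j = 3) | 92.5% | 2.3 to 2.5 |
| 40 | 6 | 85.0% | 87.2% | 87.4% (j = 4) | 87.5% | 2.2 to 2.5 |
| 40 | 8 | 80.0% | 82.1% | 82.3% (j = 5) | 82.5% | 2.1 to 2.5 |
| 26 | 4 | 84.6% | 88.0% | 88.3% (j = 3) | 88.5% | 3.4 to 3.8 |
| 26 | 8 | 69.2% | 72.0% | 72.5% (j = 5) | 73.1% | 2.8 to 3.8 |

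**Step 3, the death counted.** If the same death is an event on the day after last contact, D events again fall by the time point with nobody censored, and the estimate returns to (n − D)/n.

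**Step 4, a less stylised check.** Simulated trials (2,000 per setting; n = 40; exponential survival; follow-up of 23 to 37 months; last contact up to 12 weeks before death) gave this mean change in 24-month OS, in points, under the SAP rule:

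| True 24-month OS | 5% of deaths undated | 10% | 20% |
|---|---|---|---|
| 90% | +0.5 | +0.9 | +1.9 |
| 80% | +0.9 | +1.8 | +3.5 |
| 70% | +1.3 | +2.5 | +5.1 |

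The SAP estimate fell below the fully dated one in under 0.5% of trials in every setting. With no undated death the two are identical.

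**The case against.** Five points can be made for the other side.

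1. **The protocol is silent.** A reader might infer that the SAP contradicts the protocol and that SAP Section 8 wrongly omits the change. The documents do not support that. Protocol 5.5.4 names living subjects as censored but does not say that nobody else may be, and a time that runs to the date of death is undefined when that date is missing. Protocol 5.4 also closes with a broad sentence against other imputation, although it stands in the safety paragraph. The SAP fills a gap. This stands. It does not make the filling sound, since the SAP already imputes death dates where only the day is missing.

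2. **There may be no such deaths.** A reader might infer that OS will be overstated. Nothing in the documents shows that an undated death has occurred or is expected. Contact is about every 12 weeks, serious events are reported within 24 hours, deaths from progression go on their own form (Protocol 6.3.5), and the SAP plans narratives for deaths. This stands and makes the bias conditional.

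3. **It is small against the noise.** One undated death among 4 to 8 already means 12.5% to 25% of deaths. At n = 40 and OS of 90%, a simple 95% half-width is 1.96 × √(0.9 × 0.1/40) = 9.3 points. OS is descriptive here, and the sample size is not based on power. This stands, but the error has a known direction and is cheap to remove.

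4. **Counting every known death could create false events.** A death dated only 2023 cannot be placed before or after a cut-off projected for about 25 August 2023 (Protocol 3.2). Dating at the earliest possible day can also place a death too early. Both stand; the fix needs a cut-off condition and a stated downside.

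5. **The randomization row.** A reader might infer that a subject lost at once would have no OS time. That does not follow. Nobody in Parts 2 and 3 is randomized, so the row applies to nobody. An early loss falls under the row for loss to follow-up or study exit and is censored at the date last known alive.

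**Conclusion.** The point holds in conditional form. A stated rule turns a known OS event into a censored observation, and the expected error is upward. Each case adds roughly 2 to 2.5 points at n = 40. That size rests on the assumed 4 to 8 deaths and on complete follow-up of the others; it is somewhat larger at the lower Part 3 sample size. The number of cases is unknown and may be zero, in which case nothing changes.

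This is a weakness in how the SAP handles something the protocol leaves open. No hypothesis test depends on it. It is still worth correcting, because the estimate would then count the event that the protocol defines. The randomization wording is a clerical matter with no consequence for the estimate.

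**What to change.** In SAP 6.2.2 and Table 2, for the primary OS analysis:

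- Count a death known to have occurred on or before the data cut-off as an event.
- If only the year is known, use the day after last contact when last contact is in that year, otherwise 1 January of that year.
- If the date is fully missing, use the day after last contact.
- If the death cannot be placed on or before the cut-off, keep the subject censored at the date last known alive.
- Use the same dates where death is a PFS or DOR event.
- Report the number of undated deaths, and show the present censoring rule as a sensitivity analysis.

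As a wording clean-up only, replace randomization and the randomization date in Table 2 with first dose and the first dose date of any study drug; PFS Table 1 already censors at first dose in its rows for missing assessments.

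The cost is a few lines of SAP text and the matching programming. The downside is an approximate and possibly early death date for a rare subject, with a slightly lower OS estimate. The sensitivity analysis shows how much that choice matters.

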6.2.3 Date Last Known Alive

If year and month of date last known alive are available but day is missing, set date to the 1st of

the month. If both month and day are missing, set date to January 1st of the year.

6.2.4 Laboratory Values Below/Above the Level of Quantification

Laboratory values below the lower level of quantification (Q) that are reported as "<Q" or "≤Q" in

the database will be imputed by Q x 0.99 for analysis purposes. However, the original value will be

reported in the listings.

Laboratory values above the upper level of quantification (Q) that are reported as ">Q" or "≥Q" in

the database will be imputed by Q x 1.01 for analysis purposes. However, the original value will be

reported in the listings.

6.2.5 PK Sample Dates

Missing dates or times may be imputed for PK samples if the missing values can be established

with an acceptable level of accuracy based on other information obtained during the visit in

question.

6.3 Software

Statistical analyses and data summary will be conducted using SAS Version 9.4 or higher.

#### 7. STATISTICAL METHODS OF ANALYSIS

#### 7.1 Subject Disposition

Enrollment for subjects in the all-treated population will be presented by region, country, and site. Subject disposition will be summarized including the following information:

- Subject status on each assigned study drug (acalabrutinib, rituximab, and/or lenalidomide)
- Primary reason for each study drug discontinuation
- Subject status on the study
- Primary reason for study exit
- Time on the study (months): (earlier of study exit date or data cutoff date first dose date of any study drug + 1)/30.4375

# 7.2 Important Protocol Deviations

Number and percentage of subjects with important protocol deviations (IPDs) will be summarized, and a listing of subjects with IPDs will be produced. IPD categories, subcategory codes, and descriptions will be defined by sponsor IPD guidance and used during the course of the study. The sponsor will review IPDs throughout the study prior to database lock. The final IPD list will be used to produce the IPD summary table and listing.

# 7.3 Baseline Data

The following demographics and baseline characteristics will be presented.

#### 7.3.1 Demographics

- Age (continuous)
- Age group (<60 versus ≥60 years; <65 versus ≥65 years; <75 versus ≥75 years)
- Sex (male, female)
- Race
- Ethnicity
- Region

#### 7.3.2 Baseline and Disease Characteristics

- Eastern Cooperative Oncology Group (ECOG) performance score (0, 1, or 2)
- Height (cm)
- Weight (kg)
- Time from initial diagnosis to first dose of any study drug (months)
- Number of prior systemic regimens (excludes maintenance, consolidation, adjuvant, and neoadjuvant therapies when reported on the case report form [CRF] as a separate record)
  - o Number of regimens (mean, standard deviation [SD], median, minimum, maximum)
  - Regimen group (1, 2, 3, 4, ≥5)
- Time from end of last prior treatment to first dose of any study drug
  - o Time (mean, SD, median, minimum, maximum)
  - Time group (≤2 years, >2 years)
- Stem cell transplant (Yes)
- Baseline B symptoms
  - Any B symptom
    - Unintentional weight loss
    - Fever over 38 °C
    - Night sweats
- Bulky disease, defined as longest diameter of any target lesion at baseline
  - o <5 cm
  - o ≥5 cm and <10 cm
  - > ≥10 cm
- Ann Arbor stage at study entry (Stage I, I-E, II, II-E, III, IV; Stage I-II, III-IV)
- Bone marrow involvement
- Lactate dehydrogenase (LDH; ≤ upper limit of normal [ULN], > ULN to 3x ULN, or ≥ 3x ULN; > ULN)
- Refractory vs relapsed to last treatment
  - Refractory is defined as best response of stable disease (SD), or progressive disease (PD), or a partial response (PR)/CR with DOR ≤6 months
  - Relapsed is defined as best response of PR/CR with DOR >6 months
- Part 2 only:
  - MZL subtype (Extranodal [Gastric MALT or Non-Gastric MALT], Nodal, Splenic)
- Part 3 only:
  - o FL Grading (Grade 1, 2, or 3a)

- o Extranodal disease (yes, no), defined as extranodal notations other than "spleen"
- Follicular Lymphoma International Prognostic Index score (FLIPI; Federico 2009), defined as the number of following factors which are true: age > 60, Ann Arbor stage ≥ 3, hemoglobin < 12 g/dL, concentration of serum LDH > ULN, number of nodal areas ≥ 4.
  - Low (score 0-1)
  - Intermediate (score 2)
  - High (score 3-5)
- O High tumor burden (yes, no) per The Groupe d'Etude des Lymphomes Folliculaires (GELF) Criteria, defined as at least one of the following: a target lesion >7 cm in diameter, three nodal target lesions >3 cm in diameter each, any B symptom, concentration of serum LDH > ULN, concentration of serum hemoglobin ≤100 g/L, neutrophil count ≤1500 cells per μL, platelet count ≤100,000 platelets per mL
- Refractory to any prior regimen containing anti-CD20 antibodies (yes, no);
   refractory is defined as best response of SD, or PD, or a PR/CR with DOR ≤6 months
- Double refractory (yes, no), defined as refractory to any prior regimen containing anti-CD20 antibodies and refractory to a prior alkylating agent-containing therapy, either in separate regimens or in the same regimen

Additional baseline characteristics may be summarized as appropriate.

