 - a. Subjects who are anti-HBc positive and who are surface antigen negative will need to have a negative hepatitis B virus (HBV) DNA polymerase chain reaction (PCR) result before enrollment. Subjects who are HBsAg positive or hepatitis B PCR positive will be excluded.
 - Subjects who are anti-HCV positive will need to have a negative PCR result before enrollment. Subjects who are hepatitis C PCR positive will be excluded.
- 17. History of allogeneic stem cell (or organ) transplantation.
- 18. This criterion was removed under Amendment 5.
- 19. Major surgery within 4 weeks before first dose of acalabrutinib.
- 20. Uncontrolled autoimmune hemolytic anemia or idiopathic thrombocytopenia purpura.
- 21. History of stroke or intracranial hemorrhage within 6 months before the first dose of acalabrutinib.
- 22. Requires or receiving anticoagulation with warfarin or equivalent vitamin K antagonist (e.g., phenprocoumon) within 7 days of first dose of study drug.
- 23. Requires treatment with proton-pump inhibitors (e.g., omeprazole, esomeprazole, lansoprazole, dexlansoprazole, rabeprazole, or pantoprazole). Note: this criterion no longer applies to subjects who have switched from acalabrutinib capsules to tablets.
- 24. Received a live virus vaccination within 28 days of first dose of study drug.
- 25. ANC <1.0 × 10^9 /L or platelet count <100 × 10^9 /L. For subjects with documented disease involvement in the bone marrow, ANC <0.50 × 10^9 /L or platelet count <30 × 10^9 /L.
- 26. Creatinine >1.5 × institutional ULN; total bilirubin >1.5 × ULN; and AST or ALT >2.5 × ULN.
- 27. Breastfeeding or pregnant.
- 28. Concurrent participation in another therapeutic clinical trial.

29. In the absence of gastric MALT (subject to inclusion criterion 2b) presence of a gastrointestinal ulcer diagnosed by endoscopy within 3 months before screening or diagnosed >3 months before screening and without confirmed resolution by endoscopy.

- 30. Received any chemotherapy, external beam radiation therapy, anticancer antibodies, or investigational drug within 30 days before first dose of study drug.
- 31. History of or ongoing progressive multifocal leukoencephalopathy (PML).

3.4.5 Inclusion Criteria Part 3

Eligible subjects will be considered for inclusion in this study if they meet **all** of the following criteria.

- 1. Men and women ≥18 years of age.
- For subjects with FL: Pathologically confirmed diagnosis of FL Grade 1, 2, or 3a that

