- 13. Ongoing immunosuppressive therapy, including systemic (e.g., IV or oral) corticosteroids within 2 weeks before the first dose of study drug. Note: Subjects may use topical or inhaled corticosteroids or low-dose steroids (≤20 mg prednisone equivalent/day for ≤2 weeks) as a therapy for comorbid conditions. During study participation, subjects may also receive systemic (e.g., IV or oral) corticosteroids as needed for treatment-emergent comorbid conditions.
- 14. Grade ≥2 toxicity (other than alopecia or laboratory value requirements mentioned in Part 3 exclusion criteria) continuing from prior anticancer therapy including radiation.
- 15. Uncontrolled active systemic fungal, bacterial, viral, or other infection (defined as exhibiting ongoing signs or symptoms related to the infection and without improvement, despite appropriate antibiotics or other treatment), or intravenous anti-infective treatment within 2 weeks before first dose of study drug.
- 16. Known history of infection with HIV.
- 17. Serologic status reflecting active hepatitis B or C infection.
 - a. Subjects who are anti-HBc positive and who are surface antigen negative will need to have a negative PCR result before enrollment. Subjects who are HBsAg positive or hepatitis B PCR positive will be excluded.
 - Subjects who are HCV antibody (anti-HCV) positive will need to have a negative PCR result before enrollment. Subjects who are HCV PCR positive will be excluded.
- 18. History of allogeneic stem cell (or organ) transplantation.

- 19. Major surgery within 4 weeks before first dose of acalabrutinib.
- 20. Uncontrolled autoimmune hemolytic anemia or idiopathic thrombocytopenia purpura.
- 21. History of stroke or intracranial hemorrhage within 6 months before the first dose of acalabrutinib.
- 22. Requires or has received anticoagulation with warfarin or equivalent vitamin K antagonist (e.g., phenprocoumon) within 7 days of first dose of study drug.
- 23. Received a live virus vaccination within 28 days of first dose of study drug.
- 24. ANC <1.0 × 10⁹/L or platelet count <75 × 10⁹/L. Subjects will only be considered eligible if peripheral blood counts can be maintained independent of growth factors or transfusions during screening.
- 25. Creatinine clearance of <60 mL/min, calculated using the formula of Cockcroft and Gault [(140-Age) * Mass (kg)/(72 * creatinine mg/dL) * 0.85 if female].

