3.5.7 Dose Modification and Discontinuation

All acalabrutinib dose modifications (Table 1 and Table 2) should be discussed with the medical monitor prior to instituting changes. For toxicities that are common to both acalabrutinib and lenalidomide, consider adjusting the dose of lenalidomide before adjusting the dose of acalabrutinib per the recommendations below:

- Grade 4 neutrophil count decreases (ANC <500/µL) for >7 days (hematopoietic colony-stimulating factors are permitted per American Society of Clinical Oncology [ASCO] guidelines] and use must be recorded on the electronic case report form [eCRF])
- Grade 3 platelet count decreases in the presence of significant bleeding
- Grade 4 platelet count decreases
- Grade 3 or 4 nausea, vomiting, or diarrhea, if persistent despite optimal antiemetic and/or antidiarrheal therapy
- Any other Grade 4 toxicity or unmanageable Grade 3 toxicity

Table 1 Drug Modification and Discontinuation Actions for Acalabrutinib (in Combination with Lenalidomide)

Occurrence	Action
1st–2nd	Hold acalabrutinib until recovery to Grade ≤2 or baseline; may restart at
100 2110	original dose level (100 mg BID)
3rd	Hold acalabrutinib until recovery to Grade ≤2 or baseline; restart at 100 mg
ord	once daily
4th	Discontinue acalabrutinib

BID=twice daily.

Table 2 Drug Modification and Discontinuation Actions for Acalabrutinib (Without

Lenalidomide)

Action
Hold acalabrutinib until recovery to Grade ≤1 or baseline; may restart at
original dose level (100 mg BID)
Hold acalabrutinib until recovery to Grade ≤1 or baseline; restart at 100 mg
once daily
Discontinue acalabrutinib

BID=twice daily.

Whenever possible, any dose adjustment of acalabrutinib should be discussed between the investigator and the Sponsor's medical monitor before implementation. The appropriate clinic staff should dispense the study drug for the new dose level and instruct the subject/caregiver about the change in dose level. Any changes to the dosing regimen must be recorded on the appropriate eCRF.

Rituximab dose modifications should follow the recommendations in the Rituxan/MabThera package insert and institutional standard practices.

Per the lenalidomide label, the dose adjustments listed in Table 3 are acceptable for lenalidomide.

Table 3 Dose Modification Actions for Lenalidomide

Toxicity	Dose Adjustment
Platelets <50 × 10 ⁹ /L:	Interrupt and follow CBC weekly

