4.1.5 Confirmation of Eligibility

Subject eligibility for enrollment will be assessed per Section 3.4. All screening procedures, unless otherwise indicated, should be completed within 21 days (Part 1) and 28 days (Parts 2 and 3) of the first dose of study drug.

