- i. Subjects should be in supine position and resting for ≥10 minutes before study-related ECGs. A 12-lead ECG will be performed in triplicate (≥1 minute apart) at screening. The calculated QTcF average of the 3 ECGs must be ≤480 ms for eligibility. If results from an unscheduled ECG are abnormal and considered clinically significant at any time, then an electrolyte panel (i.e., calcium, magnesium, and potassium) must be obtained to coincide with the ECG testing.
- j. Women of childbearing potential must have two negative pregnancy tests prior to the first dose of lenalidomide. The first pregnancy test should be performed 10 to 14 days before the first dose and the second test within 24 hours prior to the first dose of lenalidomide. Pregnancy tests should be performed weekly in the first month and then monthly thereafter until 4 weeks after discontinuation of lenalidomide.
- k. Hematology includes complete blood count with differential and platelet counts. Cycle 1 Day 1 hematology does not need to be repeated if screening hematology was within 5 days.
- I. Serum chemistry: Albumin, alkaline phosphatase, alanine transaminase, aspartate aminotransferase, bicarbonate, blood urea nitrogen, bone-specific alkaline phosphatase, calcium, chloride, creatinine, glucose, lactate dehydrogenase, magnesium, phosphate/phosphorus, potassium, sodium, total bilirubin, total protein, and uric acid. Only at

- baseline: Creatinine clearance >60 mL/min. Cycle 1 Day 1 serum chemistry does not need to be repeated if screening serum chemistry was within 5 days.
- m. Hepatitis serology must include HBsAg, anti-HBs, anti-HBs, and HCV antibody. Subjects who are anti-HBc positive should have PCR testing for HBV DNA performed during screening and monthly thereafter. Monthly monitoring should continue until 12 months after last dose of study drug(s). Any subject with a rising viral load (above lower limit of detection) should discontinue study drug and have antiviral therapy instituted and a consultation with a physician with expertise in managing hepatitis B. Subjects with a known history of hepatitis C or who are hepatitis C antibody positive should be tested for HCV RNA during screening. No further testing beyond screening is necessary if PCR results are negative.
- n. Urinalysis: pH, ketones, specific gravity, bilirubin, protein, blood, and glucose. Cycle 1 Day 1 urinalysis does not need to be repeated if screening urinalysis was within 5 days.

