**6.1 Definitions** 

6.1.1 Definition of Baseline and Post-Baseline Value

Baseline is defined as the last measurement taken prior to the first dose of any study drug. A post-

baseline value is defined as a measurement taken after the first dose of any study drug.

For assessments on the day of first dose where time is not captured, a nominal pre-dose indicator,

if available, will serve as sufficient evidence that the assessment occurred prior to first dose.

Assessments on the day of first dose where neither time nor a nominal pre-dose indicator are

captured will be considered prior to first dose if such procedures are required by the protocol to be

conducted before first dose.

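### The platelet cut-off in the Part 3 high-tumor-burden definition (SAP 7.3.2) is written per mL, 1,000 times too low to be usable

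*SAP*

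**What the plan says.** SAP 7.3.2, under the items for Part 3 only, defines high tumor burden per the GELF criteria as meeting at least one of seven items: a target lesion over 7 cm; three nodal target lesions over 3 cm each; any B symptom; LDH above the upper limit of normal; low hemoglobin; low neutrophils; low platelets. The last two stand side by side as "neutrophil count ≤1500 cells per μL" and "platelet count ≤100,000 platelets per mL".

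The resulting yes/no variable is used twice. It is a Part 3 baseline characteristic (SAP 7.3.2), and it is one of the subgroups in the Part 3 forest plots of ORR, median DOR and median PFS (SAP 9.2). SAP 9 describes those plots as ad hoc analyses for a manuscript or congress presentation.

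Protocol 3.4.6, criterion 24 (repeated in the synopsis) excludes from Part 3 any subject with "ANC <1.0 × 10⁹/L or platelet count <75 × 10⁹/L". Neither document restates the GELF platelet item, and SAP 8, which lists changes from the protocol, does not mention it.

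**The concern.** Two blood-count limits in one sentence carry units that differ by a factor of 1,000, and the platelet limit falls far below any count an enrolled subject could plausibly have. Followed literally, the definition loses one of its seven items without notice.

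Because any single item is enough, the loss matters only for a subject whose sole qualifying item is a low platelet count. That subject would be counted as not high burden in the baseline table and placed in the wrong forest-plot stratum. If the programmer instead uses the sensible limit without saying so, the classification is right but departs from the SAP with no record of the change.

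**Working it through.** **Inputs**
- Written platelet limit: 100,000 per mL (SAP 7.3.2).
- Neighbouring neutrophil limit: 1,500 per μL (SAP 7.3.2).
- Part 3 platelet eligibility floor: 75 × 10⁹/L (Protocol 3.4.6, criterion 24).
- Lowest absolute platelet threshold found in either document: "or platelet count <30" × 10⁹/L, for marrow-involved subjects (Protocol 3.4.4, criterion 25; the same value is in 3.4.2 for Part 1). It does not govern Part 3 and serves only as a reference point for scale.

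The plan gives no calculation for this item, so there is no figure to reproduce. The check is a unit conversion.

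**Conversion**
- Per mL to per L, multiply by 10³: 100,000 × 10³ = 1.0 × 10⁸ per L = **0.1 × 10⁹/L**.
- Per μL to per L, multiply by 10⁶: 100,000 × 10⁶ = 1.0 × 10¹¹ per L = **100 × 10⁹/L**.
- Ratio: 100 / 0.1 = 1,000.
- Neutrophil item: 1,500 × 10⁶ = 1.5 × 10⁹/L.

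**Comparison with the other thresholds**
- Part 3 floor over written limit: 75 / 0.1 = 750.
- Lowest platelet threshold over written limit: 30 / 0.1 = 300.
- The other absolute neutrophil and platelet thresholds are given in × 10⁹/L or per μL. An example of the latter is "Grade 4 neutrophil count decreases (ANC <500" per μL in Protocol 3.5.7. None is per mL.

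**Who could be misclassified**
- Read literally, the item requires platelets ≤0.1 × 10⁹/L, while eligibility requires ≥75 × 10⁹/L at screening. The two ranges do not overlap.
- Read per μL, the item requires ≤100 × 10⁹/L, so a window of 75 to 100 × 10⁹/L is open to eligible subjects.
- Formally, the two readings disagree for baseline platelets above 0.1 and up to 100 × 10⁹/L with none of the other six items present. In practice this means about 75 to 100.
- The lower end is not strict. Protocol 4.1.5 says screening procedures "should be completed within 21 days (Part 1) and 28 days (Parts 2 and 3) of the first dose of study drug". Appendix 6, footnote k adds that "Cycle 1 Day 1 hematology does not need to be repeated if screening hematology was within 5 days". In SAP 6.1.1, "Baseline is defined as the last measurement taken prior to the first dose of any study drug". A baseline count taken after screening can therefore be somewhat below 75, but it would have to fall 750-fold from the floor to reach the written limit.

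**Reach**
- The SAP 9.2 forest-plot list has 12 subgroups, of which this is one.
- Part 3 plans about 26 to 32 subjects (SAP 3.2), so one misclassified subject is 1/32 = 3.1% to 1/26 = 3.8% of the part.

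**The case against.** The strongest objection is that the fault may lie in the extracted text and not in the SAP. The same text has other look-alike substitutions: in SAP 7.5.3 the unit of cumulative dose appears as g for acalabrutinib and q for lenalidomide; SAP 7.7.3 has T/8/NK for T/B/NK; and the reference list has Oneal for Oncol. A μ read as m would be the same kind of slip. That the μ of the neutrophil item was read correctly a few words earlier makes a misread less likely but does not exclude it. This part of the objection stands, and it is why the correction depends on the printed page.

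Second, a programmer is unlikely to use the limit literally. SAP 7.7.3 reports central-laboratory hematology in international units, so the limit has to be converted, and 0.1 × 10⁹/L would look impossible beside a floor of 75. That is a fair prediction, but it relies on someone noticing and leaves the SAP disagreeing with the program.

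Third, the consequence is very small. That is correct, and it sets the severity; it does not make the written unit right.

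Finally, no passage gives per μL for platelets. It is inferred from the neighbouring neutrophil unit and from the eligibility floor, with which it gives a range that subjects can actually occupy.

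**Conclusion.** The point holds as a minor one. As the text reads, the platelet limit is 0.1 × 10⁹/L, 1,000 times below the same number per μL and 750 times below the Part 3 eligibility floor. One of the seven items is therefore inoperative; the other six still work.

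The possible error is confined to subjects with baseline platelets of about 75 to 100 × 10⁹/L and no other qualifying item. The documents give no basis for estimating how many there are, and there may be none. Only the Part 3 baseline characteristic and one of 12 ad hoc subgroups use the variable.

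The conclusion rests on two assumptions: that the printed page says mL, as the extracted text does, and that the intended unit is per μL. Confidence is medium because the first has not been confirmed.

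**What to change.** Check the unit on the printed page of SAP 7.3.2. If it reads mL, change it to μL and add the limit in the laboratory's reporting unit, ≤100 × 10⁹/L. Confirm that the program deriving the Part 3 high-tumor-burden variable uses that limit, and that the SAP 9.2 subgroup takes its values from the same variable. If the page already prints μL, nothing needs to change.

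The cost is one unit in the SAP and a check of one line of code.
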